10.5 Site Selection, Participation, and Management

This study will be undertaken at one site, with enrollment of up to 50 subjects. The Sponsor has determined that the Principal Investigator and their staff have the facilities and expertise required. The selected site has a sufficient volume of patients who meet the inclusion and

HelpWear Inc. (CONFIDENTIAL)

no exclusion criteria, is able and willing to follow this clinical study protocol (including the collection of data, and has a staff member who can serve as a research coordinator).

10.5.1 Clinical Monitoring Procedures

Site Monitors may be used and will be managed by the Sponsor. They will have relevant experience in clinical trials involving cardiac conditions. Monitors will be chosen, based on monitoring experience in medical devices, preferably with IDE/ITA trial experience. These individuals have experience in GCP/ICH guidelines for conducting clinical studies. At a minimum, these individuals hold the credentials equivalent to that of a Clinical Research Associate (CRA).

10.5.2 Site Monitoring Procedures

Prior to study initiation, the Sponsor will develop a site monitoring plan. Monitoring the study will consist primarily of site qualification and initiation, remote monitoring of the case report forms (CRFs) and ongoing on-site monitoring and source verification.

10.5.3 On-site Monitoring

A representative of the Sponsor will visit the Investigator periodically for the purpose of monitoring the progress of this study and data collection within the chosen electronic data capture (EDC) system, in accordance with current Good Clinical Practice regulations. These include but are not limited to assuring subjects are protected, study data integrity, and compliance with applicable regulations. Any additional requirement imposed by the monitor or other regulatory authorities shall also be followed.

It is the responsibility of the Investigator to be present or available for consultation during such scheduled monitoring visits. During these routine visits, all medical source data pertaining to a patient's participation in this clinical investigation must be made available to the monitor. Medical source data are any medical records associated with the subject's health prior to study initiation and change in health during the study period.

On-site review of eCRFs focuses primarily on source verification, a comparison of data entered into the eCRF vs. source records. eCRF data points will undergo source verification using a risk-based approach that will be outlined a study-specific clinical monitoring plan. The Sponsor, or Sponsor's authorized representatives, will also review study files, including the administrative and regulatory files, subject binders and all source documentation for review in order to verify the accuracy and completeness of the records, as well as appropriate subject consent procedures.

The Investigator and appropriate personnel may be invited to attend meetings/workshops organized by the Sponsor to assure acceptable protocol execution. The study may be subject to audit by the Sponsor, Sponsor's representatives, or by regulatory authorities. If such an audit is announced or occurs, the Investigator must agree to allow access to required patient records. By signing this protocol, the Investigator grants permission to qualified personnel from the Sponsor, its authorized representatives, and appropriate regulatory authorities for on-site monitoring of all appropriate study documentation, as well as on-site review of the procedures employed in CRF generation, where clinically appropriate.

HelpWear Inc. (CONFIDENTIAL)

At study termination, a monitor will conduct an on-site study closeout visit, the purpose of which is to review all study documents and CRFs and prepare this information for proper storage.

Monitoring visits will occur as appropriate and commiserate with subject enrollment. The frequency of monitoring visits will be determined by ongoing evaluation of site performance and level of enrollment.

10.5.4 Training

All physicians and support staff who will participate in this study will undergo orientation by the Sponsor prior to study initiation at the site. Training consists of:

- Review of the study protocol
- Review of the HeartWatch device Instructions for Use
- Product Training log for study staff

10.6 Data Collection

10.6.1 Event Recorder and Holter Data

A standard 1 or 2-lead Sirona Event Recorder will be used to collect high-resolution data. Subjects will be asked to wear the clinical monitor for at least 48 hours and no longer than 84 hours. ECG signals will be continuously collected as long as the skin patches are attached to the skin and the recorder is properly connected to the wires.

A standard 5-lead SEER Holter will be used to collect 3-channels of high-resolution data. Subjects will be asked to wear the clinical, conventional monitor for at least 36 hours and no longer than 60 hours. During this time ECG signals will be continuously collected.

Specific variables of interest within both ambulatory recordings are:

- Symptoms during the extended ambulatory ECG monitoring assessment
- ECG data during the extended ambulatory ECG monitoring assessment
- Usability of the extended ambulatory ECG monitoring assessment tests
- Adverse events related to the extended ambulatory ECG monitoring tests
- User preference of the ambulatory ECG monitoring tests assessed

10.6.2 Clinical Data

Basic data related to each subject's medical history and their medications will be collected:

- Demographic (age, sex, race)
- Indication for extended ambulatory ECG testing
- Medical history

All data will be managed as per the outlined procedures in Section 8, Data Management.

11.0 Statistical Analysis Plan

11.1 Statistical Considerations

This is a preliminary study to assess the feasibility of conducting a larger multi-centre study. The objectives of this study are largely logistical (see 8.6, demonstrate the capacity to collect and pair user-triggered and auto-triggered ECG data from the HeartWatch and Event

HelpWear Inc. (CONFIDENTIAL)

Recorder and the capacity to collect and pair continuous ECG data from the HeartWatch and Holter monitor). As such, only a limited number of subjects need to be enrolled. The sample size and statistical plan are based on the comparison of the paired data.

11.2 Primary Measure of Study Success

The capacity to collect clinically-interpretable paired data. The criteria for evaluation include:

1. Ability to collect, pair, and analyze at least 20 user-triggered HeartWatch and Event Recorder ECGs.
2. Ability to collect, pair, and analyze at least 20 auto-detected HeartWatch and Event Recorder ECGs.
3. Ability to collect, pair, and analyze at least 200 hours of HeartWatch and Holter data.
4. Assess adverse events with the HeartWatch, Event Recorder, and Holter
5. Assess user preference for the HeartWatch, Event Recorder, and Holter.

11.3 Sample Size

A total of 50 patients will be enrolled to collect the required number of events in Arm A (20 triggered and 20 auto-detected) and 200 hours of continuous ECG data. This sample size takes into account that up to 20% of the data may be uninterpretable. Although we expect that less than 10% of the data will be missing or uninterpretable, a more conservative estimate is being used given the uncertainties involved in this preliminary study.

Up to 40 patients will be enrolled in Arm A, providing a sufficient number of triggered and auto-triggered events. While patients undergoing extended ECG monitoring have an unpredictable number of events, clinical observations indicate that ~25% of patients will have events, with an average of 3 triggered and 3 auto-detected events per recording. Thus, the 40 patients will provide up to 30 triggered and up to 30 auto-detected events. Assuming 20% of the data may be missing or uninterpretable, ~24 triggered and ~24 auto-detected events will be available for analysis.

Up to 10 patients will be enrolled in Arm B, providing over 250 hours of continuous ECG data. This will provide over 200 hours of usable data, assuming 20% of the data may be missing or uninterpretable.

11.4 Statistical Analysis

The purpose of this study is to collect data to allow for paired data evaluation. As such, descriptive statistics will be employed. Standard statistical methods will be used. It is anticipated that the following techniques may be used: descriptive summary statistics, Student's t-test, Chi-square, Fisher's exact test, analysis of variance, analysis of covariance, and graphical displays.

11.5 Safety Evaluation

All adverse events reported in the study will be tabulated for all subjects enrolled. Events will be tabulated by severity and relationship. Latent events will be tabulated separately. Adverse events will be evaluated and described as outlined in Section 13.

HelpWear Inc. (CONFIDENTIAL)

11.6 Usability Endpoint Analyses

Behavioral qualitative data from the product usability testing sessions will be assessed separately. In addition, all subjects participating in Study A and Study B will be asked to complete a brief questionnaire on device preference (Figure 3).

Please check off the box above the statement that best described your experience?				
				
Strongly prefer chest monitor	Slightly prefer chest monitor	No preference of monitor	Slightly prefer arm monitor	Strongly prefer arm monitor
Numeric values assigned to the subjects' response.				
-2	-1	0	1	2

Figure 3: Extended ECG Monitoring Test Preference.

User preference will be summarized and values ranging from -2 to +2 (Figure 3, lower panel) assigned to the subject's selection.

12.0 Risk Management

12.1 Adverse Events

Information on all adverse events (non-serious, serious and unanticipated events, device deficiencies) will be collected for the entire duration of the Study

12.2 Recording Adverse Events, Device Deficiencies and Protocol Deviations

All adverse and serious adverse events will be recorded on the adverse event case report form. Information to be collected and recorded will include event description, onset and resolution dates, severity, interventions performed (including the administration of pharmaceuticals) and the Investigator's assessment of relatedness to the investigational procedure and treatment.

The Sponsor or Sponsor's designee may also identify reportable events during audits or monitoring visits. Each event will be followed until resolved or stabilized at a level acceptable to the Investigator and the Sponsor's medical monitor, if utilized.

All deficiencies, anticipated or not, will be recorded on the device deficiency event case report form. Information to be collected and recorded will include the date of device deficiency, a detailed description of the deficiency and actions taken due to deficiency, model and serial number.

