	
• Symptoms during the extended ambulatory ECG monitoring assessment• ECG data during the extended ambulatory ECG monitoring assessment• Usability of the extended ambulatory ECG monitoring assessment devices• Adverse events related to the extended ambulatory ECG monitoring devices• User preference of the ambulatory ECG monitoring devices being assessed
Criteria for Evaluation:	
1. Ability to collect, pair, and analyze at least 20 user-triggered HeartWatch and Event Recorder ECGs.2. Ability to collect, pair, and analyze at least 20 auto-detected HeartWatch and Event Recorder ECGs.3. Ability to collect, pair, and analyze at least 200 hours of HeartWatch and Holter data.4. Assess adverse events with the HeartWatch, Event Recorder, and Holter5. Assess user preference for the HeartWatch, Event Recorder, and Holter.

6. Background

Heart rhythm disorders are common and significantly impact the lives of those affected and their families. The four main problems are: a) atrial fibrillation or AF, b) supra-ventricular tachycardia or SVT, c) excessively slow heart beats (i.e., bradycardia or pauses) and d) ventricular arrhythmias.

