8.0 Study Overview

This proof of concept study will enroll consecutive patients referred for extended ambulatory ECG testing. All clinical decisions will be based on data from the clinical comparator devices (i.e., Event Recorder or Holter) and the approved software analysis systems for those devices. Neither the HeartWatch data nor the paired ECG signal analyses will be used for clinical decision-making.

Subject flow is shown in **Figure 1**. Subjects will wear the HeartWatch and an Event Recorder for up to 72 hours (**Figure 1, arm A**) or the HeartWatch and Holter monitor for up to 48 hours (**Figure 1, arm B**). Subjects will be asked to document their activities (standing, sitting, walking, exercise, or laying down). Event Recorder subjects (**arm A**) will collect user-triggered and auto-triggered data, while Holter subjects (**arm B**) will record diary information on their activities and any relevant symptoms. Adverse events and user preference for one device versus the other being used in that arm will also be collected from all subjects.

In Arm A, the HeartWatch triggered and auto-detected data will be compared to single or two-lead triggered and auto-detected data Event Recorder data. Subjects will be required to wear both the HeartWatch and ambulatory Event Recorder for a 72-hour period. In Arm B the HeartWatch continuous ECG data compared to continuous ECG Holter data. Subjects will be required to wear both the HeartWatch and Holter for a 48-hour period.

All participants will be required to provide written, informed consent.

[figure not shown]

Figure 1. Study overview

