8.4 Ancillary Research Questions

Collect initial data to estimate the following:

- a) Incidence of adverse events among the HeartWatch and comparator devices,
- b) The types of adverse events that may occur, and
- c) User preferences of subjects with the HeartWatch versus the comparator devices.

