8.7 Endpoints

A. Primary endpoints:

1. User-triggered (tagged) and auto-triggered ECG data from the HeartWatch and Event Recorder.
2. Continuous ECG data from the HeartWatch and Holter monitor.

B. Secondary endpoints

1. Incidence of adverse events.

The HeartWatch is anticipated to have a similar rate of adverse events as compared to the Event Recorder and Holter monitor.

2. User preference for the extended ECG monitoring test.

The HeartWatch is anticipated to be similarly preferred to the Event Recorder and Holter monitor.

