8.10 Study Schedule of Assessments

The study's schedule of events is shown in **Table 2**. Details of assessments are provided. Information captured in assessments will be documented in study- case report forms.

Table 2. Schedule of Assessments

Study Requirement	Screening	Study	Adverse events
Informed consent	X		
Medical history and medications	X		
Eligibility criteria assessment	X		
Reason(s) for extended ECG testing	X		
Symptoms during extended ECG testing		X	
Activities during extended ECG testing		X	

Adverse events related to ECG testing			X
Usability of ECG monitoring tests		X	
User preference of ECG monitoring tests		X	

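### Adverse events are to be compared by device, but the relatedness named in 12.2 does not separate the two devices worn together; 10.2 and 10.3 also disagree on follow-up

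*Protocol*

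**What the plan says.** **What is wanted.** Three places in the protocol ask for adverse events by device.
- Section 8.4(a) seeks "Incidence of adverse events among the HeartWatch and comparator devices".
- Section 8.7 makes incidence a secondary endpoint and adds: "The HeartWatch is anticipated to have a similar rate of adverse events as compared to the Event Recorder and Holter monitor".
- Section 11.2, item 4, is "Assess adverse events with the HeartWatch, Event Recorder, and Holter".

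**How the devices are worn.** Both are worn at the same time. For Arm B, section 8.0 says: "Subjects will be required to wear both the HeartWatch and Holter for a 48-hour period". Arm A does the same with the Event Recorder for 72 hours.

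**What is recorded.** Section 12.2 lists event description, dates, severity, interventions and the investigator's "assessment of relatedness to the investigational procedure and treatment". Elsewhere the events are described only collectively: "Adverse events related to the extended ambulatory ECG monitoring devices" (synopsis), "Adverse events related to ECG testing" (Table 2 in 8.10) and "Adverse events related to the extended ambulatory ECG monitoring tests" (10.6.1).

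**How it is tabulated.** Section 11.5 tabulates events by severity and relationship, puts latent events in a table of their own, and refers to Section 13 for how events are evaluated and described.

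**When events are sought.** Section 10.2 has adverse events assessed at the return visit. It then requires a phone call one to three days after the devices are returned, to find events not apparent at return. Section 10.3 says there is no follow-up past the study period, which it gives as 72 hours for Arm A and 48 hours for Arm B.

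**The concern.** When two devices are worn together, the design does not assign an event to either of them. The assignment is a judgement, best made by the investigator when the event is recorded. If the form follows 12.2 and asks only about the investigational procedure and treatment, that judgement need not be made per device. A later analysis plan cannot restore it and would have to infer the device from the event description. The quantity at stake is a secondary endpoint and one of five evaluation criteria, meant to give initial estimates before a larger study.

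The timing conflict raises a different question. The call in 10.2 exists to find late events, but under 10.3 it is unclear whether an event first found at that call belongs to the study's adverse event data.

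**Working it through.** **Attribution: the passages side by side**

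1. Subjects wearing two devices: 40 (Arm A) + 10 (Arm B) = 50 of up to 50 (11.3). No subject wears one device alone, so no event is attributed by design.
2. The phrase in 12.2 has two objects, procedure and treatment. Splitting it into two fields would still not separate the HeartWatch from the Event Recorder or Holter. The comparator is the clinically indicated test (8.9.2), so it is uncertain whether the word investigational covers it.
3. The collective wording in the synopsis, Table 2 and 10.6.1 shows that comparator events are meant to be captured. It does not say that each event is assigned to one device or the other.
4. Section 11.5 does not say what the relationship is to. Section 13 covers site, IRBs, consent and confidentiality; its one mention of adverse events is the duty in 13.2 to keep the IRB and Sponsor informed. Recording of adverse events is in Section 12.
5. The protocol does separate the devices elsewhere: preference is scored chest monitor against arm monitor (11.6), and device deficiencies carry model and serial number (12.2).

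Effect on the comparison: let k be the number of events that cannot be placed. Each may belong to the HeartWatch only (+1), the comparator only (−1), or both or neither (0). The HeartWatch-minus-comparator count can then shift by anything from −k to +k. The protocol gives no adverse event rate, so k cannot be estimated.

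**Ascertainment: timing of the call**

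Inputs: nominal wear of 72 h and 48 h (8.0, 9.1, 9.3); permitted wear of 48 to 84 h in Arm A and 36 to 60 h in Arm B (10.6.1); call one to three days, or 24 to 72 h, after return (10.2); limits of 72 h and 48 h (10.3). The return time is not stated, so return at the end of wear is an assumption.

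Call time = wear + 24 h to wear + 72 h. Excess = call time − limit in 10.3.

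| | Arm A | Arm B |
|---|---|---|
| Nominal wear: call | 72+24 = 96 h to 72+72 = 144 h | 48+24 = 72 h to 48+72 = 120 h |
| Excess | 24 to 72 h | 24 to 72 h |
| Permitted wear: call | 48+24 = 72 h to 84+72 = 156 h | 36+24 = 60 h to 60+72 = 132 h |
| Excess | 0 to 84 h | 12 to 84 h |

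Over the whole permitted range the call never falls before the limit. It falls exactly on it in one case only: shortest wear and earliest call in Arm A. Return later than the end of wear only widens the gap. The latent-event table in 11.5 also presupposes ascertainment after wear.

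**The case against.** **On attribution.** The list in 12.2 states what recorded information will include and is not closed, and the case report form is not shown. It may already hold a device field. A reader might infer that 12.2 fixes a single relatedness field, or that comparator events would get no relatedness judgement at all. The documents support neither: the number of fields is not stated, and the synopsis, Table 2 and 10.6.1 speak of events related to the devices or tests together.

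The named risks are also mostly local: irritation where the arm band touches the skin (8.11.2), and irritation or discomfort from gel patches (8.11.3), with electrodes placed on the chest (9.1, 9.3). The description would often show which device was responsible. Table layout alone can be left to an analysis plan.

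These points limit the effect. What remains is that the one attribution the protocol does name does not match its by-device aims, and that non-local events have no body site from which to infer the device.

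**On timing.** Section 10.3 may mean only that there is no further follow-up phase. Read strictly, it would also shut out the return visit, since data are downloaded after the 72 or 48 hours. The call in 10.2 is specific and will probably be made, and 12.1, which collects events for the whole study, contradicts neither section. This is fair, but 10.3 makes no exception for the call, so the text still needs reconciling.

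The wrong section reference in 11.5 is clerical and adds no weight to the attribution point.

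**Conclusion.** Both parts hold as limited points.

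**Attribution.** The by-device adverse event summary is weakened, mainly for events without a clear body site. A reader might go further and conclude that the comparison in 8.7 cannot be made; the open list, the unseen form and the local nature of the main named risks do not support that. Every recorded event in up to 50 subjects needs attribution, but how many would lack it is unknown. The endpoint is descriptive and the paired-ECG criteria are unaffected.

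**Ascertainment.** Sections 10.2 and 10.3 contradict each other as written. The gap is 24 to 72 h if devices are returned at nominal wear, and 0 to 84 h (Arm A) or 12 to 84 h (Arm B) if they are returned at the end of any permitted wear. These hours measure the mismatch in the text; they do not show that any event would be lost.

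The change should be made because it is cheap and a judgement not recorded per device cannot be recovered later.

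**What to change.** - **12.2:** record the investigator's relatedness to the HeartWatch and to the comparator as two separate items for each event. Attribution of non-local events will still be a judgement; the two items make sure it is recorded.
- **11.5:** tabulate by device within arm (HeartWatch, comparator, both, neither) and point the cross-reference to Section 12.
- **10.2 and 10.3:** reconcile them so that the end of adverse event ascertainment is stated once, in line with the latent-event table in 11.5. Keep it distinct from the rule in 12.2 for following events already found.

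Optional: a body-site field, and a time point for adverse events in Table 2.

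Cost: one more form item (if the form now has a single relatedness item), one table layout, one corrected reference and short text edits. The form change needs no extra visit.

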12.3 Reporting Requirements

Any serious adverse events (SAEs) or UADEs that may occur must be reported by the Principal Investigator to their Institutional Review Boards, and per 21 CFR 812.150(b)(1). The Investigator will obtain, in writing, the requirements for reporting such events and file requisite documentation along with the Study documents. Serious Adverse Events should be reported to the local Institutional Review Board (IRB) per local policy. In addition, all

HelpWear Inc. (CONFIDENTIAL)

SAEs and UADEs must be reported to the Sponsor within 24 hours of the Investigator's (or other Study staff) knowledge of the event. The reporting individual shall telephone the Sponsor to report all known details at that time; if no live telephone conversation is possible, the reporting individual shall leave a telephone message followed by an electronic mail (email) transmission of all known details to the Sponsor.

Within three (3) days of the Investigator's knowledge of the SAE or adverse device effect, the appropriate adverse event case report form should be entered in the EDC system and accompanying source documentation shall be sent to the Sponsor (or the authorized representative). The Sponsor will be responsible for reporting as applicable per the statutory reporting requirements.

